Both durvalumab and tremelimumab have well established toxicity profiles as a single agent and in combination. However, the combination of durvalumab tremelimumab and palliative radiation has not been previously studied, this study will include a formal safety analysis in the first 6 patients accrued. Enrollment will be halted until these first 6 patients complete the first two cycles of treatment (8 weeks), and are evaluable for acute toxicities (toxicities reported within the 1st 8 weeks after treatment initiation). Specifically, if 2 or more DLTs (Refer to Section 6.4) are observed, then, durvalumab dosing will be modified to 1500 mg IV Q6 weeks x 9 doses and tremelimumab 75mg IV Q6 weeks x 3 doses for the remaining 14 patients (fixed dosing for patients > 30kg). If 1 or fewer DLTs are observed, then an additional 14 patients will be enrolled and treated at the initial dose and schedule of durvalumab and tremelimumab. Patients in the run in phase who experience DLTs will undergo dose modifications described in Appendix 1.

Toxicities will be graded based on CTCAE v. 4 and summarized as the number and percentage of patients with each type of toxicity. Responses will be summarized as frequencies and percentages. The Kaplan Meier method will be used to estimate overall survival and progression free survival. Outcomes will be calculated from the date of study entry to the date of the corresponding event.

We will use multivariate statistics to test the hypotheses that pretreatment intratumoral immune cell phenotype and PD-L1 expression predict response to therapy, and that therapy alters systemic immunophenotype.

Sample Size Determination:

There are multiple ongoing studies in various tumor types exploring the activity of durvalumab and tremelimumab. In a published report of the combination in patients with advanced NSCLC treated on a phase Ib study, Grade 3-4 toxicity was observed in 17% of patients. Similarly, in single institution reports of SBRT with the monoclonal antibody, grade 3 or higher toxicity was reported in 6-16% of patients. With a 20 patient accrual goal, toxicity rates can be estimated to within 22% with 95% confidence. Any toxicity with at least 10% prevalence has at least an 87% chance of being observed. This design allows us to reasonably exclude a clinically significant increase in toxicity with the addition of radiation therapy to the durvalumab and tremelimumab combination as defined by the upper bound of the confidence interval.

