3.3 Study Oversight for Safety Evaluation

The primary endpoint of this study is safety and tolerability. Durvalumab and tremelimumab will be given at the recommended fixed dosing in patients > 30kg (see section 1.3.1), which has been shown to result in minimal toxicity, but encouraging efficacy in NSCLC patients. Since the concurrent administration of radiation therapy is previously unstudied in this cohort, the first 6 patients will represent a run-in phase, and enrollment will be halted until all patients complete

the first two cycles of treatment (8weeks) These 6 patients will be assessed for DLTs and will determine if a modified dosing schedule of durvalumab and tremelimumab will be applied in the expansion phase.

In keeping with the study primary endpoint, a stopping rule will be implemented in the unlikely event that the combination under study is deemed to have unacceptably high toxicities. Enrollment will be halted if more than 3 patients experience a Grade 4 or higher drug related toxicity (CTCAE v. 4) during the trial or up to 30 days after the last investigational drug infusion. The likelihood of observing 3 or more Grade 4+ drug-related DLTs is 80% if the true rate is 20% and the likelihood is 91% if the true rate is 25%. This rule has an 83% chance of stopping in the 1st 10 patients if the true rate is 40%. Section 10.2.2 provides some guidelines on the attribution of toxicity to the drug and radiation combination. The study will be reviewed by the University of Washington/Fred Hutchinson Cancer Research Center Data Safety and monitoring board.

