6.2. Dosage and Administration

The treatment to be used in the run in phase of this trial for patients > 30kg is outlined in the Table below:

Drugs	Dose/Potency	Dose Frequency	Route of Administration	Regimen/Treatment Period
1. Durvalumab	1500 mg	Q4 weeks	IV infusion	Maximum of 13 doses
2. Tremelimumab	75mg	Q4 weeks	IV infusion	Maximum of 4 doses

If 2 or more DLTs (defined in Section 6.4) are observed in the run-in phase, the following treatment will be used for the remaining 14 patients to be treated on the clinical trial protocol:

Drugs	Dose/Potency	Dose Frequency	Route of Administration	Regimen/Treatment Period
1. Durvalumab	1500 mg	Q6 weeks	IV infusion	Maximum of 9 doses
2. Tremelimumab	75mg	Q6 weeks	IV infusion	Maximum of 3 doses

Patients who experience a DLT in the run in phase, will have dose interruptions/modifications as outlined in Appendix 1.

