6.4 Definition of DLT

Dose-limiting toxicities (DLTs) will be evaluated during the run in phase consisting of the first 6 patients enrolled in this trial. The period for evaluating DLTs will be from the time of first administration of durvalumab or tremelimumab until 28 days (cycle 1). Adverse event monitoring will continue for these subjects throughout the course of their treatment (beyond cycle 1) as outlined in the Schedule of Study Assessments, these adverse events will include potential XRT related toxicities. Subjects who do not remain on the study up to this time for reasons other than DLT will be replaced with another subject. Grading of DLTs will follow the guidelines provided in the Common Terminology Criteria for Adverse Events (CTCAE) version 4.0.

A DLT will be defined as any Grade 3 or higher toxicity that occurs during the DLT evaluation period. Toxicity that is clearly and directly related to the primary disease or to another etiology is excluded from this definition. The following will be DLTs:

- Any Grade 4 irAE
- Any \geq Grade 3 colitis
- Any Grade 3 or 4 noninfectious pneumonitis irrespective of duration
- Any Grade 2 pneumonitis that does not resolve to \leq Grade 1 within 3 days of the initiation of maximal supportive care
- Any Grade 3 irAE, excluding colitis or pneumonitis, that does not downgrade to Grade 2 within 3 days after onset of the event despite optimal medical management including systemic corticosteroids or does not downgrade to \leq Grade 1 or baseline within 14 days
- Liver transaminase elevation $> 8 \times$ ULN or total bilirubin $> 5 \times$ ULN
- Any \geq Grade 3 non-irAE, except for the exclusions listed below
 - Grade 3 fatigue lasting \leq 7 days
 - Grade 3 endocrine disorder (thyroid, pituitary, and/or adrenal insufficiency) that is managed with or without systemic corticosteroid therapy and/or hormone replacement therapy and the subject is asymptomatic
 - Grade 3 inflammatory reaction attributed to a local antitumor response (eg, inflammatory reaction at sites of metastatic disease, lymph nodes, etc)
 - Concurrent vitiligo or alopecia of any AE grade
 - Grade 3 infusion-related reaction (first occurrence and in the absence of steroid prophylaxis) that resolves within 6 hours with appropriate clinical management

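### The 28-day DLT window in Section 6.4 does not match the 8-week run-in evaluation it serves, and DLT evaluability does not depend on receiving radiation

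*Combined protocol and SAP*

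**What the plan says.** Section 6.4 fixes the window: "The period for evaluating DLTs will be from the time of first administration of durvalumab or tremelimumab until 28 days (cycle 1". It then builds that window into the definition: "A DLT will be defined as any Grade 3 or higher toxicity that occurs during the DLT evaluation period". Monitoring of adverse events, including possible radiation effects, continues beyond cycle 1, but Section 6.4 does not add those later events to the DLT count.

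The synopsis (Statistical Methods and Data Analysis) holds enrollment until the first six patients have completed two cycles and "are evaluable for acute toxicities (toxicities reported within the 1st 8 weeks after treatment initiation". Its next sentence applies the decision rule: "if 2 or more DLTs (Refer to Section 6.4) are observed", the other 14 patients go to the 6-weekly schedule. Section 6.2 repeats the rule: "If 2 or more DLTs (defined in Section 6.4) are observed in the run-in phase". Section 3.3 also puts the 8-week hold directly before the DLT assessment: "the first two cycles of treatment (8weeks) These 6 patients will be assessed for DLTs".

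On who counts, Section 4.4 replaces a DLT-free run-in patient who received less than 90% of the cycle 1 infusion. Section 6.4 adds: "Subjects who do not remain on the study up to this time for reasons other than DLT will be replaced with another subject". Neither section mentions radiation. Section 3.2 describes the run-in as one of all three components, and Section 3.3 gives the reason for it: "Since the concurrent administration of radiation therapy is previously unstudied in this cohort, the first 6 patients will represent a run-in phase".

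**The concern.** The run-in count is the only prespecified trigger for changing the drug interval. Whether a Grade 3 event between day 29 and day 56 counts toward it depends on which window applies. The synopsis and Section 3.3 lead a reader to expect 8 weeks; the definition they point to says 28 days.

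The shorter window also suits the purpose poorly. Radiation is the new element and starts only in week 3, so most of a 28-day window has passed before the three-part treatment has been given in full.

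The evaluability rules raise a second problem. They test drug exposure and time on study but not radiation. A patient who never starts radiation says little about the combination, yet can enter the denominator of six as a patient without a DLT.

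**Working it through.** The protocol states no operating characteristic for the 2-of-6 rule, so there is no figure to reproduce. The check is a comparison of the text plus day arithmetic.

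**1. Which window feeds the count.** Both statements of the rule (synopsis, Section 6.2) refer to Section 6.4, where the 28-day limit is part of the definition. The 8 weeks in the synopsis attaches to the enrollment hold and to acute toxicities. On the cross-references, 28 days governs the count. No sentence says, however, that the two periods serve different purposes, and the DLT rule follows directly on the 8-week evaluation.

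**2. Section 6.4 against itself.** Section 6.4 lists a delay of more than 2 weeks in starting cycle 2, caused by treatment-related toxicity, as a DLT. In the text as extracted this item follows the list of exclusions, but it stands next to death from toxicity, so it can only be meant as a DLT.
- Cycle 2 is due on day 1 + 28 = day 29.
- A delay of more than 14 days is known only after day 29 + 14 = day 43.
- 43 > 28, so the criterion cannot be met inside the stated window. 43 < 56, so it fits inside 8 weeks.

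**3. Observation after radiation.** Radiation starts 2 weeks after first dose (synopsis), which is day 15. Three fractions every other day (synopsis, Section 5.3.3) fall on days 15, 17 and 19.

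| Course | Last day | To day 28 | To day 56 |
|---|---|---|---|
| Fractions on days 15, 17, 19 | 19 | 28 − 19 = 9 days | 56 − 19 = 37 days |
| Full 2 weeks (Schedule of Study Assessments) | 28 | 28 − 28 = 0 days | 56 − 28 = 28 days |

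If 28 elapsed days are meant, the first entry becomes 29 − 19 = 10 days.

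**4. What happens to a later Grade 3 event under the 28-day reading.**
- An event first arising after cycle 2 has started is outside the DLT definition. It is also outside the stopping rule in Section 3.3, which counts only Grade 4 or higher drug-related toxicity.
- A toxicity that holds back cycle 2 by more than 2 weeks is a listed DLT.
- Either event is known before expansion, because enrollment is on hold for 8 weeks.

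**5. Evaluability.** Take a patient with the full cycle 1 infusion, no radiation, on study at day 28 and without a DLT. Neither the Section 4.4 condition nor the Section 6.4 condition is met, so the patient is not replaced and counts as one of six without a DLT. A patient who leaves between day 29 and day 56 for another reason is likewise not replaced under Section 6.4, although the hold requires two completed cycles.

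**6. Illustration only.** Let the 17% Grade 3-4 rate in Section 11.3 stand in for an 8-week DLT rate, and let s be an assumed share arising after day 28. With X ~ Bin(6, q) and q = 0.17 × (1 − s), P(X ≥ 2) = 1 − (1 − q)^6 − 6q(1 − q)^5:
- s = 0: q = 0.17, giving 0.271
- s = 0.25: q = 0.1275, giving 0.172
- s = 0.5: q = 0.085, giving 0.086

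The 17% comes from lung cancer patients on the drug pair and is not a DLT rate; the documents give no value for s. These figures show direction and carry no weight in the conclusion.

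**The case against.** The strongest defence is that there are two windows for two purposes. Section 6.4 is the defining section, both statements of the rule refer to it, and the 8 weeks is an enrollment pause with a wider look at acute toxicity. As a reading of the count, this stands. A reader might infer that the protocol leaves the two windows on an equal footing; the cross-references do not support that. The defence does not explain the cycle 2 delay criterion, and it leaves about 9 days after radiation to inform the decision.

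A second defence is that later events do not go unseen. Enrollment is on hold to week 8, data are reviewed weekly (Section 14), a monitoring committee oversees the study (Section 13.2.1), and it can be terminated for safety (Section 13.3). This stands too. A reader might infer that no Grade 3 event from day 29 can count, or that such events escape notice. The cycle 2 delay criterion contradicts the first and the hold contradicts the second. What remains is the lack of a prespecified trigger.

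On radiation, every patient is planned to receive it, planning takes place at screening, and completing two cycles of treatment could be read to include it. That makes omission less likely. But completion of two cycles is a condition for lifting the hold and does not name radiation; it is not a rule on who counts for DLTs.

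Finally, replacing everyone with incomplete radiation would remove patients who stopped because they could not tolerate it. That objection is right, and the remedy has to allow for it.

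**Conclusion.** The concern holds in this form. The count is best read as running for 28 days, but that window conflicts with the 8-week evaluation described around it and with a criterion in the same section. It leaves about 9 days after the last fraction instead of about 37, assuming radiation is given on days 15, 17 and 19. Under that reading, a Grade 3 event first arising after cycle 2 starts is seen but feeds neither the DLT count nor the stopping rule. Independently of the window, a run-in patient without radiation can count as DLT-free; the documents give no basis for estimating how often that would happen.

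This should be corrected, because the count sets the schedule for 14 of the 20 planned patients. It does not show that the run-in would reach the wrong decision, or by how much the chance of de-escalation would change. That would need an 8-week DLT rate and a late share, and the documents give neither.

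**What to change.** In Section 6.4, set the DLT window to 8 weeks (56 days) from first dose, matching the existing hold. In Sections 6.4 and 4.4, state that a run-in patient without a DLT is replaced if either applies:
- the planned radiation (3 fractions at 8 Gy, or at the 6 Gy permitted in Section 5.3.3) was not received, for reasons other than treatment-related toxicity;
- the patient was not followed to week 8.

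Keep in the count any patient who stopped radiation because of treatment-related toxicity. Align the 2-week radiation entry in the Schedule of Study Assessments with the 1 week in the synopsis, and say whether replacements count toward the maximum of 20.

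The cost is wording in two sections and one schedule cell. The hold is no longer for patients treated as planned. Each replacement restarts an 8-week observation period. Because Section 11.1 counts replaced patients as enrolled and the synopsis caps enrollment at 20, a replacement may also use one of the 20 − 6 = 14 expansion places unless the cap is raised.

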3.2 Study Schema

The first 6 patients of this study will represent the initial run-in phase of the triplet combination of durvalumab, tremelimumab and HIGRTor SBRT. Fixed doses of Durvalumab and Tremelimumab will be administered on day 1 of therapy. Radiation will be initiated on Week 3 of the 28 day cycle. Radiation will be delivered to a total dose of 24 Gy, given in 3 fractions of 8Gy every other day. Durvalumab will be continued for a total of 13 cycles, and tremelimumab for a total of 4 cycles unless patient withdraws consent, has confirmed disease progression, and/or develops toxicity that results in treatment discontinuation.

Serum correlative studies will be collected at the following timepoints: at baseline, prior to cycle #2, and prior to cycle#4 of treatment. Archived formalin fixed paraffin embedded tissue will be collected from patients enrolled. If the patient does not have archived tissue available, a fresh biopsy will be obtained.

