 - Grade 3 or 4 neutropenia that is not associated with fever or systemic infection that improves by at least 1 grade within 3 days. Grade 3 or Grade 4 febrile neutropenia will be a DLT regardless of duration or reversibility

- Grade 3 or 4 lymphopenia
- Grade 3 thrombocytopenia that is not associated with clinically significant bleeding that requires medical intervention, and improves by at least 1 grade within 3 days
- Isolated Grade 3 electrolyte abnormalities that are not associated with clinical signs or symptoms and are reversed with appropriate maximal medical intervention within 3 days
- Prolonged delay (>2 weeks) in initiating cycle 2 due to treatment-related toxicity
- Grade 5 toxicity, i.e. death

Dose modification/delays according to Section 6.5.1 and Appendix 1 will apply to the patients who experience DLTs in the run in phase.

Immune-related AEs are defined as AEs of an immune nature (ie, inflammatory) in the absence of a clear alternative etiology. In the absence of a clinically significant abnormality, repeat laboratory testing will be conducted to confirm significant laboratory findings prior to designation as a DLT.

6. 5 Dose Modification and Toxicity Management

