Grade 2 (stool frequency of 4 to 6 over baseline per day)	Hold study drug/study regimen until resolution to Grade ≤1 • If toxicity worsens, then treat as Grade 3 or Grade 4.		
For Grade 2:
 
 Consider symptomatic treatment, including hydration, electrolyte replacement, dietary changes (eg, American Dietetic Association colitis diet), and loperamide and/or budesonide.

Specific Immune-mediated Reactions

Adverse Events	Severity Grade of the Event (NCI CTCAE version 4.03)	Dose Modifications	Toxicity Management
		
 • If toxicity improves to Grade ≤ 1, then study drug/study regimen can be resumed after completion of steroid taper. 	
 – Promptly start prednisone 1 to 2 mg/kg/day PO or IV equivalent. – If event is not responsive within 3 to 5 days or worsens despite prednisone at 1 to 2 mg/kg/day PO or IV equivalent, GI consult should be obtained for consideration of further workup, such as imaging and/or colonoscopy, to confirm colitis and rule out perforation, and prompt treatment with IV methylprednisolone 2 to 4 mg/kg/day started. – If still no improvement within 3 to 5 days despite 2 to 4 mg/kg IV methylprednisolone, promptly start immunosuppressives such as infliximab at 5 mg/kg once every 2 weeks. Caution: it is important to rule out bowel perforation and refer to infliximab label for general guidance before using infliximab. – Consult study physician if no resolution to Grade ≤ 1 in 3 to 4 days. – Once the patient is improving, gradually taper steroids over ≥ 28 days and consider prophylactic antibiotics, antifungals, and anti-PCP treatment (refer to current NCCN guidelines for treatment of cancer-related infections [Category 2B recommendation]).^a
Grade 3 or 4 (Grade 3: stool frequency of ≥ 7 over baseline per day; Grade 4: life threatening consequences)	Permanently discontinue study drug/study regimen.	For Grade 3 or 4:	
 – Promptly initiate empiric IV methylprednisolone 2 to 4 mg/kg/day or equivalent. – Monitor stool frequency and volume and maintain hydration. – Urgent GI consult and imaging and/or colonoscopy as appropriate. – If still no improvement within 3 to 5 days of IV

Specific Immune-mediated Reactions

Adverse Events	Severity Grade of the Event (NCI CTCAE version 4.03)	Dose Modifications	Toxicity Management

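### Section 6.4 closes DLT evaluation at Day 28 but lists a cycle 2 delay first met about Day 44, without saying whether onset or fulfilment must fall in the window

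*Combined protocol and SAP*

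**What the plan says.** Section 6.4 sets the window: "The period for evaluating DLTs will be from the time of first administration of durvalumab or tremelimumab until 28 days (cycle 1"). Its general definition is tied to when the toxicity happens: "A DLT will be defined as any Grade 3 or higher toxicity that occurs during the DLT evaluation period". The itemised list that follows includes "Prolonged delay (>2 weeks) in initiating cycle 2 due to treatment-related toxicity". In the extracted text this item comes after the exclusions, but its content, and the fatal-toxicity item beside it, show that it is meant as a DLT.

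Two other places give a longer period for the same six patients. The synopsis (Statistical Methods and Data Analysis) makes them evaluable for "toxicities reported within the 1st 8 weeks after treatment initiation" and then applies the DLT rule with a reference to Section 6.4. Section 3.3 holds enrollment until all six complete "the first two cycles of treatment (8weeks") and says that they are assessed for DLTs.

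Under the synopsis and Section 6.2, two or more DLTs in the run-in move the remaining 14 patients to a different schedule.

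Appendix 1 bears on how long cycle 2 may be held. For Grade 2 diarrhea/enterocolitis that improves, "then study drug/study regimen can be resumed after completion of steroid taper". The taper instruction in the same row, "Once the patient is improving, gradually taper steroids over", is followed by a minimum of 28 days.

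**The concern.** A DLT item that needs more than 14 days of delay after the end of cycle 1 sits in a list whose evaluation period ends with cycle 1. The toxicity can start well inside the window while the test that makes it a DLT is met only later. Section 6.4 does not say which date decides.

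This goes beyond whether a new toxicity starting on Days 29 to 56 counts. Here the toxicity has already started in cycle 1. A patient whose cycle 2 is on hold but who remains on study past Day 28 is not replaced under 6.4, so on a strict reading that patient enters the six as DLT-free. At stake is the one decision that the run-in exists to make: the schedule for 14 of the 20 patients.

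**Working it through.** **Inputs.** Cycle length 28 days (Section 3.2: "Radiation will be initiated on Week 3 of the 28 day cycle"). DLT period 28 days and delay threshold of more than 14 days (6.4). Hold of two cycles, 8 weeks (synopsis, 3.3). Visit windows of ±3 and ±7 days (Schedule of Study Assessments; the table is broken in the extracted text, so both are tried). Taper of at least 28 days (Appendix 1). Decision rule: 2 or more DLTs in 6 patients.

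**1. The plan's own figure.** 2 × 28 = 56 days = 8 weeks. This reproduces.

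**2. Earliest fulfilment, nominal schedule.** First dose is Day 1, so cycle 2 is due on Day 1 + 28 = Day 29. The first whole day beyond a 14-day delay is 29 + 15 = Day 44. That is 44 − 28 = 16 days after the last day of the DLT period and 56 − 44 = 12 days before the end of the 8 weeks.

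**3. Sensitivity to convention.** Earliest day = due day + 15:

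| Shift of due day | First dose = Day 1 | First dose = Day 0 |
|---|---|---|
| −7 days | 37 | 36 |
| −3 days | 41 | 40 |
| none | 44 | 43 |
| +3 days | 47 | 46 |
| +7 days | 51 | 50 |

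Every value is later than Day 28 and earlier than Day 56.

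**4. Another item with the same gap.** A Grade 3 immune-related event also becomes a DLT if it has not reached Grade 1 or baseline within 14 days. With onset on day d this is settled on day d + 14, which is after Day 28 whenever d > 14.

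**5. Are such delays foreseeable?** Where Appendix 1 ties redosing to completing the taper, a taper starting on day s gives redosing no earlier than s + 28, so the delay is at least s + 28 − 29 = s − 1 days. For s = 15 it is 14 days (not met); for s = 16, 15 days (met); for s = 20, 19 days; for s = 28, 27 days. Radiation begins in Week 3, nominally Day 15.

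**6. One record, two counts.** Take Grade 2 diarrhea starting in cycle 1, with the taper begun on Day 20 and redosing no earlier than Day 48, a delay of at least 19 days. It is not Grade 3 colitis and meets no other listed item. If fulfilment must fall by Day 28, it adds 0 DLTs. If onset decides, it adds 1. With one other DLT among the six, the total is 1 or 2, and the schedule for the remaining 14 differs.

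**7. How steep the rule is.** With counted DLT probability p per patient, independent patients and at most one DLT each, P(2 or more of 6) = 1 − (1 − p)^6 − 6p(1 − p)^5. At p = 0.20 this is 1 − 0.262 − 0.393 = 0.345. Over an assumed range:

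| p | P(2 or more of 6) |
|---|---|
| 0.10 | 0.114 |
| 0.15 | 0.224 |
| 0.20 | 0.345 |
| 0.25 | 0.466 |
| 0.30 | 0.580 |

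Each 5 points on the counted rate move the chance of the modified schedule by 11 to 12 points. These rates are illustrations; the documents state no DLT rate and no operating characteristics for this rule.

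**The case against.** The best reply is that 6.4, read naturally, already counts the delay. Its definition sentence asks when the toxicity occurs, not when each consequence is complete. The delay item requires the delay to be caused by treatment-related toxicity, so a cycle 1 toxicity that later holds up cycle 2 fits both sentences. The list also goes beyond the general sentence elsewhere (it counts some Grade 2 pneumonitis), so a specific item should not be emptied by the general clause. All six patients are in any case watched for 8 weeks, which covers Day 44. Much of this stands. A reader might infer that the delay item can never be counted; the documents do not support that, because it follows only if fulfilment itself must fall by Day 28.

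A second reply is that this is one consequence of the conflict between 28 days and 8 weeks. That is partly right, and the two should be fixed together. But choosing a window does not by itself say whether onset or fulfilment must fall in it. With an 8-week window, the 14-day test for a Grade 3 immune-related event starting on Day 43 would still run to 43 + 14 = Day 57.

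Third, a reader might infer that every steroid-treated event from mid-cycle 1 automatically becomes a DLT. The documents do not go that far. Section 6.5.1 says the dose guidance may be applied, Appendix 1 is framed as recommendation, and Grade 2 hepatitis receives steroids only if it persists or worsens. That a delay criterion depends on the start day is inherent in such a criterion and is not an error.

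**Conclusion.** The point holds as an unresolved conflict within 6.4, and between 6.4 and the synopsis and Section 3.3. On the nominal schedule the delay item is first met on Day 44, against a DLT period ending on Day 28; no day-numbering or visit-window convention brings it inside. Two defensible readings give different DLT counts from the same records, and a difference of one patient can change the schedule for 14.

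The calendar result rests only on 28-day cycles and the stated thresholds. The frequency of the problem cannot be sized. It might be tempting to start from the 17% Grade 3-4 rate in the sample-size section and add a few percent for delay events, but that rate comes from a lung cancer study of the two drugs, is not given as a 28-day DLT rate, and the documents supply nothing to add to it. The steepness figures above show only that the 2-of-6 rule is sensitive to what is counted. This should be settled before the run-in count is taken; it does not show that the run-in is invalid.

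**What to change.** Reconcile the 28-day period in 6.4 with the 8-week period in the synopsis and Section 3.3, so that one window governs the run-in decision. Then add to 6.4 a rule to this effect: *delay-based and duration-based items (the cycle 2 delay and the 14-day test for Grade 3 immune-related events) are attributed to the onset date of the causing toxicity; they count if that onset lies inside the evaluation window, even when they are fulfilled later; the DLT count is taken at the end of the 8-week hold.*

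The cost is a few sentences. With a 28-day onset window no time is added: the delay item matures by Day 51 at the latest and the 14-day test by 28 + 14 = Day 42, both before Day 56. If the sponsor chooses 8 weeks as the onset window, a Grade 3 immune-related event starting after Day 42 could still be pending when the count is taken, and 6.4 should say how that is handled. The small downside is that the run-in may count slightly more DLTs than under a strict 28-day reading.

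Whether a delay caused only by finishing a steroid taper should count is a design choice for the sponsor. No change to taper, dose or schedule is proposed.
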